Title: A Randomized, Controlled, Double-Blind, Parallel-Group, Phase 3 Study to Compare the Pharmacokinetics, Efficacy and Safety between CT-P10, Rituxan and MabThera in Patients with Rheumatoid Arthritis

Clinical Phase: Phase 3

Study Design: Randomized, controlled, multicenter, 3-arm, double-blind, parallel-group, prospective, pharmacokinetic (PK), efficacy, pharmacodynamic (PD), and safety study.

Part 1: PK similarity

Part 2: Efficacy similarity

Planned Number of Centers/Countries: It is expected that up to approximately 110 study centers in Europe, Asia Pacific, and Latin America may be included in this study.

Test Formulation, Dose, and Regimen: CT-P10, 1000 mg by intravenous (IV) infusion. Each patient may receive 3 courses (2 courses in the Main Study Period and 1 course in the Extension Study Period) of treatment if the patient meets predefined safety criteria. Each course consists of 2 infusions with a 2-week interval between the first and second infusion. Methotrexate (MTX) (between 7.5 and 25 mg/week orally or parenterally [dose and route must be maintained from beginning to end of study]) and folic acid (\geq 5 mg/week) will be coadministered.

Reference Drug, Dose, and Regimen: Rituxan (United States-licensed) or MabThera (European Unionapproved), 1000 mg IV infusion. Each patient may receive 3 courses (2 courses in the Main Study Period and 1 course in the Extension Study Period) of treatment if the patient meets predefined safety criteria. Each course consists of 2 infusions with a 2-week interval between the first and second infusions. Methotrexate (between 7.5 and 25 mg/week orally or parenterally [dose and route must be maintained from beginning to end of study]) and folic acid (\geq 5 mg/week) will be coadministered.

Objectives:

All patients from Part 1 of the study will be included in Part 2 of the study and undergo all assessments performed in Part 2.

The decision to enter Part 2 of the study will not be influenced by the results from Part 1.

Part 1

Primary objective:

• To evaluate and compare pharmacokinetics in terms of area under the serum concentration-time curve from zero to time of last quantifiable concentration (AUC_{0-last}), AUC from zero to infinity (AUC_{0- ∞}) and maximum serum concentration (C_{max}) (after the second infusion) of CT-P10 to Rituxan, CT-P10 to MabThera and Rituxan to MabThera during the first course of treatment (over the first 24 weeks).

Secondary objectives:

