Co-primary PK endpoints: The primary PK analysis will assess the similarity of CT-P10, Rituxan and MabThera in terms of AUC_{0-last} (over both infusions of the first course of treatment, from time zero to the last measurable concentration), AUC_{0- ∞} (over both infusions of the first course of treatment, from time zero to infinity) and C_{max} (after the second infusion in the first course of treatment) as co-primary PK endpoints. The primary PK parameter estimates will be analyzed using an analysis of covariance (ANCOVA) with treatment as a fixed effect and country, gender, race, prior anti-TNF-alpha (anti-TNF- α) blocker status (inadequate response versus intolerant case), and RF or anti-CCP status (both positive versus both negative versus either RF or anti-CCP negative) fitted as covariates. If country is found to be unsuitable as a covariate due to the number of levels, then this may be pooled into a new variable, region defined in the statistical analysis plan (SAP), for use as a covariate. Point estimates (geometric means and ratio of geometric means) will be calculated from back transforming the least squares means of the natural log-transformed values of AUC_{0-last}, AUC_{0- ∞} and C_{max}. AUC_{0-last}, AUC_{0-∞} and C_{max} will be natural log-transformed prior to analysis, and 90% confidence intervals (CIs) for the ratio of the geometric means of the 2 treatments (CT-P10 versus Rituxan, CT-P10 versus MabThera, and Rituxan versus MabThera) will also be produced. Similarity will be demonstrated if the 90% confidence interval (CI) for the geometric mean ratio of CT-P10 to Rituxan and MabThera in AUC_{0-last}, AUC_{0-∞} and C_{max} is within the bounds of 80% and 125%. AUC_{0-last}, AUC_{0-∞} and C_{max} will be summarized by treatment. Summary statistics will include the n, mean, standard deviation (SD), median, minimum, maximum, geometric mean, and coefficient of variation (CV). In Part 1, based on overall 90% power, a type I error of 0.1, an interpatient CV in AUC_{0-last} of 30%, 50 patients are needed in each treatment group being compared (50 patients in the CT-P10 treatment group, 50 patients in the Rituxan treatment group, and 50 patients in the MabThera treatment group; 150 patients in total). Allowing for a drop-out rate of 20%, 189 patients will be randomly assigned into the study in a 1:1:1 allocation.

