2.1 Primary Objectives

2.1.1 Primary Objective: Part 1

The primary objective of Part 1 of the study is:

• To demonstrate similar pharmacokinetics in terms of AUC_{0-last}, AUC_{0-∞} and C_{max} (after the second infusion) of CT-P10 to Rituxan, CT-P10 to MabThera, and Rituxan to MabThera during the first course of treatment (over the first 24 weeks).

2.1.2 Primary Objective: Part 2

The primary objective of Part 2 of the study is:

• To demonstrate that CT-P10 is similar to reference products in terms of efficacy as determined by clinical response according to change from baseline in disease activity measured by Disease Activity Score using 28 joint counts (DAS28) (C-reactive protein [CRP]) at Week 24.

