7.5 Sample Size Calculations

Part 1 of this study is powered to demonstrate PK similarity of CT-P10, Rituxan and MabThera in AUC_{0-last}, AUC_{0- ∞} and C_{max}. Similarity will be demonstrated if the 90%

confidence interval (CI) for the geometric mean ratio of CT-P10 to Rituxan and MabThera in AUC_{0-last} , $AUC_{0-\infty}$ and C_{max} is within the bounds of 80% and 125%.

In Part 1, based on overall 90% power, 2-sided alpha equal to 0.1, an interpatient coefficient of variation (CV) in AUC_{0-last} of 30%, and a true of geometric mean equal to 1, fifty patients are needed in each treatment group being compared (50 patients in the CT-P10 treatment group, 50 patients in the MabThera treatment group, and 50 patients in the Rituxan treatment group: 150 patients total). The statistical power of each comparison, CT-P10 versus MabThera, CT-P10 versus Rituxan and MabThera versus Rituxan is 96.5% to achieve overall 90% power accounting for multiplicity with type II error correction. Allowing for a drop-out rate of 20%, 189 patients will be randomly assigned into the study in a 1:1:1 allocation.

In Part 2, the sample size of 322 evaluable patients (133 patients in the CT-P10 group and 189 patients in the reference products group [Rituxan and MabThera groups]) leads to approximately 90% power for the demonstration of similarity based on a two-sided 90% CI for the difference of mean change of DAS28 score at Week 24 from baseline value between CT-P10 and reference products for an equivalence margin of ± 0.50 . In the sample size calculation, the common standard deviation of the mean change of DAS28 at Week 24 from baseline is assumed as 1.32 based on the CT-P10 1.1 study result for the therapeutic equivalence margin of ± 0.50 . Incorporating hypothesized drop-out rate of 10%, total sample size of 361 subjects (149 eligible patients in the CT-P10 and 212 eligible patients in the reference products group [Rituxan and MabThera groups], including up to 63 patients from each of the CT-P10, Rituxan and MabThera groups in Part 1) will be used in evaluation of efficacy endpoints.

In total, approximately 361 patients will be available for analysis (a total of approximately 149 patients for the CT-P10 group and 212 patients for the reference products group, including up to 63 patients from each treatment group in Part 1).

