- The similarity of pharmacokinetics between CT-P10, Rituxan and MabThera will be concluded if the 90% CIs for the ratios of geometric means based on all the combinations of the three treatments in a pairwise comparison are entirely contained within 80% to 125% for AUC_{0-last}, AUC_{0-∞}, and C_{max}. The equivalence margin of 80% 125% is the universal standard PK similarity margin.

Serum concentrations of study drugs will be summarized by treatment at each scheduled collection time. In addition to the standard summary statistics, the geometric mean and CV will also be presented at each time point. Mean serum concentration time profiles of study drugs will be plotted by treatment on linear and semilogarithmic scales based on scheduled sample times. Individual concentrations and scheduled and actual sample times will be presented in data listings by treatment.

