### 5.2. Sample Size

For Part 1, 189 patients will be randomized in a 1:1:1 ratio to the CT-P10, Rituxan, and MabThera groups. Later, for Part 2, 172 patients will be allocated in a 1:1 ratio to the CT-P10 and Rituxan groups.

Part 1 of this study is powered to demonstrate PK similarity of CT-P10, Rituxan, and MabThera in  $AUC_{0-last}$ ,  $AUC_{0-\infty}$ , and  $C_{max}$ . Similarity will be demonstrated if the 90% confidence interval (CI) for the geometric mean ratio of CT-P10 to Rituxan and MabThera in  $AUC_{0-last}$ ,  $AUC_{0-\infty}$ , and  $C_{max}$  is within the bounds of 80% and 125%.

In Part 1, based on overall 90% power, Two one-sided alpha equal to 0.05, an interpatient CV in  $AUC_{0-last}$  of 30%, and a true of geometric mean equal to 1, fifty patients are needed in each treatment group being compared (50 patients in the CT-P10 treatment group, 50 patients in the MabThera treatment group, and 50 patients in the Rituxan treatment group: 150 patients total). The statistical power of each comparison, CT-P10 versus MabThera, CT-P10 versus Rituxan,

and MabThera versus Rituxan is 96.5% to achieve overall 90% power accounting for multiplicity with type II error correction. Allowing for a drop-out rate of 20%, 189 patients will be randomly assigned into the study in a 1:1:1 allocation.

In Part 2, the sample size of 322 evaluable patients (133 patients in the CT-P10 group and 189 patients in the reference products group [Rituxan and MabThera groups]) leads to approximately 90% power for the demonstration of similarity based on a two-sided 90% CI for the difference of mean change of DAS28 (CRP) score at Week 24 from baseline value between CT-P10 and reference products for an equivalence margin of  $\pm 0.50$ . In this sample size calculation, the common standard deviation of the mean change of DAS28 at Week 24 from baseline is assumed as 1.32 based on the CT-P10 1.1 study result for the therapeutic equivalence margin of  $\pm 0.50$ . Incorporating hypothesized drop-out rate of 10%, total sample size of 361 subjects (149 eligible patients in the CT-P10 and 212 eligible patients in the reference products group, including up to 63 patients from each of the CT-P10, Rituxan, and MabThera groups in Part 1) will be used in evaluation of efficacy endpoints.

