### 10.3. Pharmacokinetic Statistical Analysis

In Part 1, the primary PK analysis will assess the similarity of CT-P10, Rituxan and MabThera in terms of  $AUC_{0-last}$ ,  $AUC_{0-\infty}$  and  $C_{max}$  over the first 24 weeks as co-primary PK endpoints.

ANCOVA will be performed for  $AUC_{0-last}$ ,  $AUC_{0-\infty}$  and  $C_{max}$  with treatment group as a fixed effect and country, gender, race, prior anti-TNF- $\alpha$  blocker status (intolerance case versus inadequate response) and RF or anti-CCP status (both positive versus both negative versus either

RF or anti-CCP negative) fitted as covariates. Clinically relevant variables at baseline are used as the covariates for adjusted means. If country is found to be unsuitable as a covariate due to the number of levels, then this may be pooled into a new variable, region (defined as either EU or Non-EU), for use in the statistical model. The  $AUC_{0-last}$ ,  $AUC_{0-\infty}$  and  $C_{max}$  will be natural log transformed prior to the analysis. Point estimates (geometric least squares means and ratios of geometric means) will be calculated by back-transforming the least squares means, and 90% CIs of the ratios (CT-P10 versus Rituxan, CT-P10 versus MabThera, and Rituxan versus MabThera) will be produced.

Similarity will be demonstrated if the 90% CI for the geometric mean ratio of CT-P10 to Rituxan and MabThera in  $AUC_{0-last}$ ,  $AUC_{0-\infty}$  and  $C_{max}$  is within the bounds of 80% and 125%.

When outliers occur at some time points, primary statistical analysis of PK parameters is carried out with data excluding observed outliers. However, a sensitivity analysis will also be performed with data including observed outliers. Additional ANCOVA for the PK primary endpoint will be conducted in patients whose ADA status result at Week 24 is “Negative” both including and excluding outliers. When there are Significant GCP non-compliance sites, an additional sensitivity analysis will be performed for PK primary endpoints.

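### The Part 1 primary PK objective has two pass rules: three pairwise comparisons in Protocol 7.8.1.1, but only the two CT-P10 comparisons in the synopsis, Protocol 7.5, SAP 5.2 and SAP 10.3

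*SAP*

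**What the plan says.** **Three-comparison rule.** Protocol 7.8.1.1 makes its conclusion of PK similarity conditional on every pairwise 90% interval: "ratios of geometric means based on all the combinations of the three treatments in a pairwise comparison are entirely contained within 80% to 125" per cent. The condition applies to each of AUC0-last, AUC0-∞ and Cmax.

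**Two-comparison rule.** The co-primary PK paragraph of the Protocol synopsis reads "Similarity will be demonstrated if the 90% confidence interval (CI) for the geometric mean ratio of CT-P10 to Rituxan and MabThera" is within 80% and 125% for the same parameters. Protocol 7.5 has the same criterion ("confidence interval (CI) for the geometric mean ratio of CT-P10 to Rituxan and MabThera"), as does SAP 5.2. SAP 10.3 repeats it: "Similarity will be demonstrated if the 90% CI for the geometric mean ratio of CT-P10 to Rituxan and MabThera". Rituxan versus MabThera is absent from all four. SAP 10.3 lists all three ratios when it says which CIs will be produced, and then leaves the reference-to-reference ratio out of the criterion.

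**Related text.**
- The objective in Protocol 2.1.1 is to demonstrate similarity of "CT-P10 to Rituxan, CT-P10 to MabThera, and Rituxan to MabThera during the first course of treatment". The synopsis and SAP 3.1.1 name the same three pairs, but under the weaker aim of evaluating and comparing.
- The power statement in Protocol 7.5 is "The statistical power of each comparison, CT-P10 versus MabThera, CT-P10 versus Rituxan and MabThera versus Rituxan is 96.5" per cent. SAP 5.2 agrees: "and MabThera versus Rituxan is 96.5% to achieve overall 90% power accounting for multiplicity with type II error correction".
- Protocol 7.8 says that changes from the protocol's analyses will be documented in the SAP. The SAP text available here records no change to this rule.

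**The concern.** These sentences decide whether a primary objective is met, and they differ in content. An analyst working from SAP 10.3 would apply six conditions (two comparisons by three parameters). A reader of Protocol 7.8.1.1 would apply nine. The conflict arises when both CT-P10 comparisons pass on every parameter and Rituxan versus MabThera fails on at least one. Protocol 7.8.1.1 then says similarity is not concluded, while the other four places say it is demonstrated. The choice between them would be made after the data are known.

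Type I error is not at issue. Each rule requires every comparison it names to pass, so neither inflates the chance of a false claim. The rules differ in what is claimed and in power. Similarity of the two references would also lend support to pooling them in Part 2, but that is an inference: no section makes pooling depend on it.

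**Working it through.** **Inputs.** From Protocol 7.5 and SAP 5.2: interpatient CV of AUC0-last 30%, true ratio 1, limits 80% to 125%, 90% CI (two one-sided tests at 0.05), 50 evaluable per arm, 96.5% power per comparison, 90% overall, 20% drop-out, 189 randomised.

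**1. Reproduce the plan's figures.**
- Log-scale SD = √ln(1 + 0.30²) = 0.2936. SE of a difference = 0.2936 × √(2/50) = 0.0587. Limit = ln 1.25 = 0.2231.
- Normal approximation: 2Φ(0.2231/0.0587 − 1.645) − 1 = 96.9%. Exact t calculation with 98 df: 96.68%. The plan states 96.5%.
- Type II split over three comparisons: 1 − 3 × (1 − 0.9668) = 90.0%. With the stated 96.5% it is 1 − 3 × 0.035 = 89.5%. The plan states 90%.
- Drop-out: 50/0.8 = 62.5, so 63 per arm and 189 in total, as stated.

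**2. Which rule was the trial sized for?** Overall power = 1 − k(1 − power per comparison), for k comparisons:

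| n per arm | Power per comparison | k = 2 | k = 3 |
|---|---|---|---|
| 45 | 94.67% | 89.3% | 84.0% |
| 46 | 95.15% | 90.3% | 85.5% |
| 49 | 96.35% | 92.7% | 89.0% |
| 50 | 96.68% | 93.4% | 90.0% |

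Fifty is the smallest size that gives 90% with three comparisons; two comparisons would need 46. The sample size was therefore built on the three-comparison rule. The figure of 46 is evidence of intent, not a proposed redesign.

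**3. How often the rules disagree, one parameter.** Simulation of three arm means with pooled variance (147 df), true ratios 1, n = 50, 2,000,000 runs: 94.03% pass under two comparisons and 91.82% under three. The rules disagree in 94.03 − 91.82 = 2.21% of trials.

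**4. Three parameters jointly.** The documents give a CV only for AUC0-last, so two assumptions are needed: CV 30% for all three parameters, and AUC0-last identical to AUC0-∞. The second is reasonable. With the half-life of about 20 days in Protocol section 1 and sampling to Day 168, a one-compartment approximation leaves about 0.4% of AUC0-∞ to extrapolate (0.06% to 2.5% for assumed half-lives of 15 to 30 days). With 300,000 runs per case:

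| Assumed correlation of Cmax with AUC | Two comparisons | Three comparisons | Disagreement |
|---|---|---|---|
| 1 | 94.05% | 91.81% | 2.24% |
| 0.8 | 90.63% | 87.33% | 3.30% |
| 0.5 | 89.07% | 85.21% | 3.86% |
| 0 | 88.29% | 84.11% | 4.18% |

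**5. If the references truly differed.** The documents give no such difference, so this is illustration only. With CT-P10 assumed midway between the references and one parameter, disagreement is 6.3%, 17.8% and 30.3% for true Rituxan/MabThera ratios of 1.05, 1.10 and 1.15.

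**The case against.** The best defence is that the short sentence is shorthand, or that Protocol 7.8.1.1, as the analysis section, stands by default over a synopsis and a sample-size paragraph when the SAP records no change. That reading is reasonable, but no text states it. The protocol contradicts itself as well as the SAP, and SAP 10.3 never gives the three-comparison rule.

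Four further points have force:

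- **Low probability.** Disagreement is about 2% to 4% at the planning assumptions, and every CI will be reported anyway. This is correct. The case rests on a primary rule needing a single answer, not on frequency.
- **The objectives are weaker evidence than they look.** Only Protocol 2.1.1 speaks of demonstrating similarity. The synopsis and SAP 3.1.1 could be read as estimating three ratios and judging CT-P10 on two. This stands, so the power calculation and Protocol 7.8.1.1 are the firmer support for three comparisons.
- **The stated 90% holds for one parameter only.** Under the joint assumptions, three-comparison power is 84% to 87% at Cmax correlations of 0 to 0.8. This also stands and should be disclosed, although two-comparison power falls too.
- **Timing.** SAP section 2 describes this SAP as serving the final analysis, while the PK primary is reported at Week 24. An earlier SAP may have governed that report, so the fix must also cover the case where unblinding has already happened.

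**Conclusion.** The concern holds. The Part 1 primary objective has two incompatible decision rules, and they give opposite conclusions whenever Rituxan versus MabThera is the only comparison to fail. At the planning assumptions this happens in 2.2% of trials for one parameter. For three parameters jointly it is about 2% to 4%, conditional on an assumed common CV of 30%, identical AUCs and a Cmax–AUC correlation between 0 and 1. It would be more frequent if the references differed, but the documents support no figure for that. The sample size itself is sound and matches the three-comparison rule. This must be fixed because a primary pass rule has to be unambiguous, even though a conflict is unlikely.

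**What to change.** Put the rule of Protocol 7.8.1.1 into the synopsis, Protocol 7.5, SAP 5.2 and SAP 10.3. Suggested wording: PK similarity is concluded if the 90% CIs for the geometric mean ratios CT-P10/Rituxan, CT-P10/MabThera and Rituxan/MabThera all lie within 80% to 125% for AUC0-last, AUC0-∞ and Cmax.

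If the sponsor intends two comparisons:
- correct Protocol 7.8.1.1 and align the objective in Protocol 2.1.1;
- label the Rituxan/MabThera CI as supportive;
- restate the power as about 93% to 94% for one parameter at 50 evaluable per arm;
- record the change in the SAP.

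Under either rule, say that the stated power refers to one parameter. Leave 189 randomised unchanged, because the Part 2 totals depend on it: 189 + 172 = 361; 63 + 86 = 149 for CT-P10; 149 + 63 = 212 for the references.

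Make the change before the Week 24 unblinding described in Protocol 5.5.1. If that has passed, the study report should state which rule was applied and show all nine CIs against both.

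The cost is wording only, with no new data, analysis or patients. Compared with the two-comparison rule, the three-comparison rule lowers the pass probability from 94.0% to 91.8% for one parameter, or by about 2 to 4 percentage points jointly.

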## **11.1. ACR20, ACR50 and ACR70 criteria**

### **11.1.1. Proportion of ACR20, ACR50, and ACR70 Responders**

The American College of Rheumatology (ACR) criteria are a standard measure of clinical activity in rheumatoid arthritis patients. The ACR criteria used in this study are ACR20, ACR50, and ACR70.

A patient is defined as a responder according to ACR20 criteria if the following are fulfilled:

- A percentage decrease of at least 20% from baseline in the number of tender joints
- A percentage decrease of at least 20% from baseline in the number of swollen joints, and
- A percentage decrease of at least 20% from baseline in three of the following:
  - Patient's assessment of pain (VAS scale, mm)
  - Patient's global assessment of disease activity (VAS scale, mm)
  - Physician's global assessment of disease activity (VAS scale, mm)
  - HAQ estimate of physical ability
  - Serum CRP (mg/dL) concentration or ESR (mm/h)

Note: Percentage change = (Post-baseline value - baseline value)/baseline value \* 100

The following categories of patients are considered non-responders at each week respectively:

- Patients with an improvement according to the ACR criteria of less than 20%
- Patients who discontinue the study prior to the week of interest
- Patients with missing data for the evaluation of ACR20 criteria at the week of interest
- Patients with protocol prohibited initiation of new or increase in dose of RA medications that are deemed to affect efficacy. The ACR response status of these patients will be determined prior to database lock on an individual basis after agreement from the medical monitoring department of [REDACTED] and the sponsor.
- Patients requiring a surgical joint procedure prior to and including the week of interest. Surgical joint procedures will be defined as those patients with a reported joint surgery on the 'Joint Surgery Yes/No' eCRF page.

Any patient not satisfying any of the responder or non-responder criteria will be assigned a non-responder status. The ACR50 and ACR70 are calculated similarly to ACR20. However, a decrease of 50% and 70%, respectively, must be achieved.

The proportion of patients demonstrating ACR20, ACR50, and ACR70 (based on 1995 ACR criteria) will be summarized for the efficacy population, efficacy – 2nd treatment course in Main

Study Period subset and efficacy – Extension Study Period subset by treatment group at each visit, accordingly.

The proportion of patients achieving clinical response according to the criteria for ACR20 at each visit will be summarized in patients whose swollen joints (of 66 assessed) and tender joints (of 68 assessed) equal to or higher than 8 at baseline by efficacy population, efficacy – 2nd treatment course in Main Study Period subset and efficacy – Extension Study Period subset.

Additionally, the proportion of patients achieving clinical response according to the criteria for ACR20 at each visit will also be summarized by Efficacy (Antibody Negative/Positive Subset).

A listing will be provided for the all-randomized population by treatment group and visit, showing ACR20, ACR50 and ACR 70 responder status at each visit.

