7.8.2.2 Secondary Efficacy Analyses

ACR20, ACR50, and ACR70

A patient is defined as a responder according to ACR20 criteria if the following are fulfilled:

- A decrease of at least 20% in the number of tender joints
- A decrease of at least 20% in the number of swollen joints, and
- A 20% improvement in 3 of the following:
 - Patient's assessment of pain on the VAS
 - Patient's global assessment of disease activity (VAS)
 - Physician's global assessment of disease activity (VAS)
 - HAQ estimate of physical ability
 - Serum CRP concentration or ESR

The VAS range is 0 to 10 cm, with higher scores indicating poorer status or more severe pain.

The following categories of patients are considered nonresponders at each week respectively:

- Patients with an improvement according to the ACR criteria of less than 20%
- Patients who discontinue the study prior to the week of interest, except for safety reasons
- Patients with missing data for the evaluation of ACR20 at the week of interest
- Patients with protocol prohibited changes in medication including initiation therapy with a new disease-modifying antirheumatic drugs, increase in dose of RA medication (MTX or corticosteroid), and administration of intra-articular corticosteroids
- Patients requiring a surgical joint procedure during the study

The ACR50 and ACR70 are calculated similarly to ACR20, however, an increase or decrease of 50% and 70%, respectively, must be achieved.

The proportion of patients demonstrating ACR20, ACR50, and ACR70 (based on 1995 ACR criteria) will be summarized by treatment at Week 24, Week 48, and Extension Week 24.

The mean change in the components of the ACR criteria from Baseline will be summarized for ACR20, ACR50, ACR70, and hybrid ACR.

Time to onset of the ACR20 response will also be summarized by treatment.

Hybrid ACR

The hybrid ACR is an outcome measure that combines the ACR20, the ACR50, and the ACR70 and a continuous score of the mean improvement in core set measures (American College of Rheumatology Committee to Reevaluate Improvement Criteria 2007). The score is determined by calculating the mean percentage change in core set measures and reading the score from Table 2 using the patient's ACR status.

	Mean % Change in Core Set Measures									
ACR Status	<20	≥20, <50	≥50, <70	≥70						
Not ACR20	mean % change	19.99	19.99	19.99						
ACR20 but not ACR50	20	mean % change	49.99	49.99						
ACR50 but not ACR70	50	50	mean % change	69.99						

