#### **5.6. Protocol Deviations**

Protocol deviation will be categorized as “major” or “other (or minor)”. Category of protocol deviation will be identified during the Data Review Meeting (DRM). A major protocol deviation is one that may affect the interpretation of study results or the patient’s rights, safety or welfare. Patients with major protocol deviation could be excluded only from the population (PD and/or Efficacy) that would be affected by the deviation.

Major protocol deviations are defined as follows:

- Mis-randomizations (defined as patients who received the another treatment to which they were assigned at any point during the study)
- Non-compliance of inclusion or exclusion criteria (to be identified by the [REDACTED] medical department via review of data sourced from the site monitoring database)
- Significant GCP non-compliance sites (to be identified by [REDACTED] as sites which have been closed due to suspected scientific misconduct and/or serious GCP non-compliance)
- Receipt of prohibited medication (based on agreement of each as from both [REDACTED] and CLT prior to database lock)

The major protocol deviations and other categories used for exclusion will be summarized for the all-randomized population by study part, treatment group. A listing of major protocol deviations for each patient will also be provided by treatment group.

The significant GCP non-compliance site will be excluded in all populations. The information of this site will be only listed in the Demographics and Treatment-emergent Serious Adverse Events listings, separately.

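### Prohibited RA medication is ACR non-response in the protocol, but the SAP gives three competing treatments and no order of precedence

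*SAP*

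**What the plan says.** **Protocol 7.8.2.2** gives a list introduced by "The following categories of patients are considered nonresponders at each week respectively". One entry is "Patients with protocol prohibited changes in medication including initiation therapy with a new disease-modifying antirheumatic drugs". The same entry goes on to dose increases of methotrexate or corticosteroid "and administration of intra-articular corticosteroids". It has no filter and no case review. Another entry is "Patients who discontinue the study prior to the week of interest, except for safety reasons", followed directly by an entry for missing ACR20 data.

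**SAP 11.1.1** opens its list in the same way: "The following categories of patients are considered non-responders at each week respectively". Its medication entry covers only new or increased RA drugs judged to influence efficacy, and continues: "The ACR response status of these patients will be determined prior to database lock on an individual basis". Agreement between a medical monitoring department and the sponsor is needed. Intra-articular corticosteroids are not named, and the discontinuation entry has no safety exemption.

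**SAP 5.6** lists among major deviations "Receipt of prohibited medication (based on agreement of each as from both" of two parties before database lock. It adds: "Patients with major protocol deviation could be excluded only from the population (PD and/or Efficacy) that would be affected by the deviation". SAP 5.4 repeats the option.

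**SAP 11** excludes patients with such medication at the affected visit for every efficacy analysis, subject to anything specified elsewhere. It bases all secondary efficacy analysis on the efficacy population and its subsets. For ACR status, SAP 11.1.1 gives the all-randomized population a listing only.

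**Protocol 7.6** removes major violators from the efficacy population, but also requires every efficacy parameter to be analysed in the all-randomized population.

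**The concern.** One event, starting or increasing a prohibited RA drug, has one ACR outcome in the protocol and up to three in the SAP: scored individually, removed with the patient, or removed with the visit. Each gives a different numerator, denominator or both. The SAP states neither an order of precedence nor criteria for the individual decision.

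The protocol counts these patients as failures. Any route that drops them or scores them as responders raises the reported rate. ACR status also feeds hybrid ACR (SAP 11.1.3) and time to ACR20 (SAP 11.1.2), which carries a log-rank p-value between CT-P10 and the combined reference group. The all-randomized analysis, where population removal could not act, is the protocol's safeguard; the SAP does not carry it over for ACR.

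**Working it through.** **Step 1. The routes side by side.**

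| Source | Treatment of the patient | Binding? |
|---|---|---|
| Protocol 7.8.2.2 | Non-responder; stays in the denominator | Yes |
| SAP 11.1.1 | Non-responder if the drug is judged to influence efficacy; status then set individually | Discretionary |
| SAP 5.4, 5.6 | May leave the efficacy population | Optional |
| SAP 11 | Excluded at the affected visit | Yes, unless specified elsewhere |

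SAP 11.1.1 is also at odds with itself: a category that is non-response by definition needs no individual determination. SAP 11.1.1 may be the exception that SAP 11 allows for, but the SAP does not say so.

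**Step 2. Size within one arm.** The documents give no ACR rate and no share on prohibited medication, so there is no stated figure to reproduce. Let q be the affected share and r the ACR20 rate in the others. Both are assumptions: q = 2 to 10%, r = 60%.

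- Non-responder rule: r(1 − q)
- Removal of patient or visit: r
- Individual scoring: from r(1 − q) up to r(1 − q) + q
- Removal minus non-responder rule: rq

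| q | Non-responder | Removal | Gap | Individual scoring, maximum |
|---|---|---|---|---|
| 2% | 58.8% | 60.0% | 1.2 | 60.8% |
| 5% | 57.0% | 60.0% | 3.0 | 62.0% |
| 10% | 54.0% | 60.0% | 6.0 | 64.0% |

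With r from 50% to 70%, rq is 1.0 to 1.4 points at q = 2%, 2.5 to 3.5 at 5%, and 5.0 to 7.0 at 10%.

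A whole-patient check uses the 133 evaluable CT-P10 patients planned in SAP 5.2. Take 7 affected and 76 responders among the other 126. The rates are 76/133 = 57.1% (non-responder), 76/126 = 60.3% (removal), and 83/133 = 62.4% (all 7 scored as responders).

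**Step 3. Size between arms.** With equal r, the difference (CT-P10 minus reference) is:

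- non-responder rule: r(q_ref − q_CT)
- removal: 0
- all affected patients scored as responders: (1 − r)(q_CT − q_ref)

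At q_CT = 10% and q_ref = 5%, these are 0.60 × (−0.05) = −3.0 points, 0, and 0.40 × 0.05 = +2.0 points. At 5% in both arms all three are zero.

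For scale, the standard error of the difference at 133 and 189 evaluable patients is √[0.6 × 0.4 × (1/133 + 1/189)] = 5.5 points. The 90% half-width is 1.645 × 5.5 ≈ 9 points.

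**The case against.** The case against has real force on several points.

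- **Removal is not new in the SAP.** Protocol 7.6 already drops major violators from the efficacy population, and Protocol 10.2.2 grades deviations in agreement with the sponsor. Removal under SAP 5.4 and 5.6 is optional. A reader might infer that the SAP orders removal against the protocol; the text does not support that. What stands is that the protocol does not itself class prohibited medication as major, and that it pairs the restricted population with an all-randomized analysis.
- **Similarity is not decided on ACR.** A reader might infer that the loose rule tilts the trial towards a similarity conclusion. That decision rests on DAS28 (CRP) against ±0.50 and on the PK intervals. ACR proportions have no margin and are only summarised. The exclusions in SAP 5.6 and 11 also reach DAS28, but no non-responder rule exists there for them to contradict.
- **Scoring as a responder is only possible.** The SAP sentence sits under a non-responder heading, and SAP 11.1.1 defaults unclassified patients to non-response. Individual review may be meant only to decide whether the drug mattered. The wording does not confine it to that, and the protocol has no such filter.
- **Unblinded scoring is not shown.** Decisions precede database lock, and Protocol 10.2.2 defines deviations before unblinding. SAP 5.3 unblinds sponsor staff for the Week 24 report, so later ACR decisions are not clearly blinded; the documents say no more than that.
- **The size is assumed.** Even the 3-point contrast needs unequal shares and lies well inside sampling error.

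**Conclusion.** The conflict stands as a defect in the rules for secondary endpoints. The protocol fixes the ACR score for these patients; the SAP leaves it open between a filtered and individually decided status, removal from the population, and removal of the visit. It also omits the all-randomized ACR summary that the protocol requires.

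Under the stated assumptions, the choice between non-responder scoring and removal is worth 1.2 to 6.0 points on an arm's ACR20 rate. Individual scoring can move that rate by up to the whole affected share. The between-arm difference is practically unchanged if the arms are affected equally. The results at risk are ACR20/50/70, hybrid ACR and time to ACR20; the DAS28 and PK similarity decisions do not use ACR status.

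Two smaller mismatches belong with it. Protocol 7.8.2.2 names intra-articular corticosteroids under non-response, SAP 11.1.1 does not, and Protocol 5.7 allows one injection after Week 24 with non-response counted for the injected joint. The protocol's exemption for safety discontinuation is undone by its own missing-data entry and is absent from the SAP.

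**What to change.** 1. **SAP 11.1.1:** for ACR, delete the individual-determination sentence and the filter on effect on efficacy. Score patients with prohibited new or increased RA medication as non-responders, as Protocol 7.8.2.2 does. State that this applies at visits on or after the change; the protocol gives no timing, so this is an addition. State that hybrid ACR and time to ACR20 use the same status.
2. **SAP 5.4, 5.6 and 11:** state that neither population-level nor visit-level exclusion for prohibited RA medication received during the study applies to ACR20/50/70. Limit this to RA medication, because the prohibited list in Protocol 5.7 is wider.
3. **SAP 11:** add the all-randomized ACR summary required by Protocol 7.6.
4. **Reconcile** the intra-articular corticosteroid wording across Protocol 5.7, Protocol 7.8.2.2 and SAP 11.1.1. Reconcile the safety-discontinuation exemption with the missing-data entry beside it and with SAP 11.1.1. Record any departure from the protocol in the SAP, as Protocol 7.8 requires.

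The cost is SAP wording, one further set of ACR tables, and a protocol clarification if its text is changed. No new data are needed. Reported ACR rates would be slightly lower.
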